6.5.2 Study Procedures

Treatment period

Visit 1 (T0): baseline/inclusion

A first specialist visit could be performed by an ENT as per common clinical practice based on patient's symptoms. In the case that the ENT performed a first diagnosis of typical upper symptoms due to GERD, the diagnosis could be confirmed according to the diagnostic process scheduled by the usual clinical practice in use at the investigational site prior to attending the Gastroenterologist or the investigator could directly send the patient to the Gastroenterologist for the confirmation of the diagnosis and for assigning an appropriate therapy. Patients sent by the ENT should not have been pre-treated with PPIs and/or medical devices and/or similar products (e.g. alginates, antacids etc...). The Gastroenterologist Investigator that recruited patients in the study collected the consent, performed and/or confirmed the first diagnosis of upper symptoms of GERD in case the patient will be sent by the ENT, and included the patients in the study provided that they had not yet received treatments for GERD. At the baseline/inclusion visit (V1, T0), patients will be instructed on the nature of the study and received any information on the risks and benefits related to study participation.

After the time to freely decide and after giving their written informed consent to study participation and to the management of personal data related to the study, patients underwent the clinical and instrumental investigations needed to assess their eligibility.

Recruited patients will be visited by a Gastroenterology specialist, who performed and/or confirmed the diagnosis of upper symptoms of GERD and recorded all the following information and results performed during the visit on a clinical record/worksheet (source document) and on the eCRF:

- Verification of inclusion/exclusion criteria, with special attention to upper symptoms of GERD;
- Demographic data (birth date, gender, race);
- Vital signs (systolic and diastolic blood pressure, heart rate, respiratory rate, weight and height with calculation of body mass index [BMI]);
- Clinical diagnosis of GERD: first diagnosis nor confirmation of first diagnosis;
- Clinical assessment of extra-oesophageal symptoms, upper symptoms associated with the diagnosis of GERD;
- Identification of the reference ENT and of his/her affiliation;
- Patient's anamnesis, with brief details of medical history and particular attention to medical history of upper symptoms (i.e. date of onset, symptoms' description, frequency and intensity of symptoms);
- Anamnesis of concomitant therapies, treatments taken in the last 4 weeks and ongoing treatments, with particular attention to remote and recent therapies, intake of PPIs and/or medical devices and/or similar products (e.g. alginates, antacids, etc..), chronic use of drugs that interfere with the salivary secretion (e.g. anti-histamines or inhaled steroids) and thus represented an exclusion criterion and other non-permitted therapies;
- Objective examination and concomitant diseases;
- Haematology and blood chemistry: haemochrome, erythrosedimentation rate (ESR), C-reactive
 protein (CRP), aspartate aminotransferase (AST), alanine aminotransferase (ALT), alkaline
 phosphatase, gamma-glutamyl transpeptidase (gamma-GT), total and direct bilirubin, glycaemia,
 creatininemia, blood urea nitrogen (BUN) (tests performed in the last 3 months will be kept as
 valid);

- The evaluation of beta-human chorionic gonadotropin (beta-hCG) levels will be performed only in women of childbearing potential;
- RSI questionnaire, completed by patients following the Investigator's explanation;
- Likert scale, completed by patients following the Investigator's explanation.

Furthermore, the Investigator:

- Explained to patients which other products could or not could be taken for the entire study duration;
- Dispensed a diary to patients, to be completed daily, explaining to patients the procedures for completion and the importance of a correct filling, recommending them to daily report the presence and intensity of upper symptoms, the amount of taken investigational product, the possible use of other products taken on-demand for the treatment of GERD and of all other products, the possible changes of dose of taken treatments and all possible adverse events or incidents occurred during the study.

Patients satisfying inclusion/exclusion criteria and that, by signing the informed consent provided at the beginning of the study, accepted to adhere to the study procedures and to complete the daily diary, will be included in the study and will be randomly allocated to the investigational product to be taken for the following 6 weeks of treatment. Thus the Investigator proceeded to:

- Patient's randomisation and assignment of a randomisation number;

- Likert scale, completed by patients during the visit;
- Questionnaire on patient's likelihood of treatment, completed by patients during the visit;
- Review of diaries and Investigator's assessment of diary entries, dispensing of new diaries and adequate recommendations for completion;
- Compliance to treatment, based on verification of diaries. In case of necessity, the patient will be re-trained;
- Use of rescue medication: used products, frequency, dosage and reasons for intake;
- Possible incidents and/or adverse events: treatments/procedures taken to treat the event/incident, duration of the event/incident and correlation with the investigational product;
- Planning with the patient of the date for the following visit V4.

Visit 4 (T6 after 6 weeks \pm 2 *days from the baseline visit): intermediate assessment*

Patients will be visited by a Gastroenterology specialist, who recorded all the following data collected during this visit in the source document and in the eCRF:

- Vital signs (systolic and diastolic blood pressure, heart rate, respiratory rate, weight and height with calculation of BMI);
- Concomitant therapies, maintenance of the ongoing therapies, new therapies or changes in frequency or dosage of ongoing therapies, with particular attention to possible intake of nonpermitted medications;
- Objective examination, by pointing into evidence possible changes from baseline;
- Assessment of upper symptoms associated with the diagnosis of GERD, by pointing into evidence possible changes from baseline;
- Haematology and blood chemistry: haemochrome, ESR, CRP, AST, ALT, alkaline phosphatase, gamma-GT, total and direct bilirubin, glycaemia, creatininemia, BUN, and changes from baseline;
- Evaluation of beta-hCG levels, only in women of childbearing potential;
- RSI questionnaire, completed by patients during the visit;
- Likert scale, completed by patients during the visit;
- Questionnaire on patient's likelihood of treatment, completed by patients during the visit;

- Review of diaries and Investigator's assessment of diary entries;
- Compliance to treatment, collection of investigational products accountability of the product returned by patient during this visit;
- Use of rescue medication: used products, frequency, dosage and reasons for intake;
- Possible incidents and/or adverse events: treatments/procedures taken to treat the event/incident, duration of the event/incident and correlation with the investigational product;
- Assessment of patients responder/non-responder to investigational products;
- End of study assessments.

Furthermore, the Investigator:

- Selected responder patients in Group 1 and treated with Gerdoff®+PPI;
- In case the patient will be willing to continue in the study, dispensed a new diary to the patient, to be completed daily for the 12-week follow-up period, further explaining the procedures of completion and the importance of a correct completion to patient, and recommending him/her to report daily the presence and intensity of upper symptoms, the amount of administered investigational product, the possible use of other products taken on-demand for the treatment of GERD, and all the other products taken, and all the possible adverse events or incidents occurred during the study.

Responder patients Group 1 (Gerdoff®+PPI) that, by signing the informed consent at the beginning of the study, accepted to attain the procedures scheduled for the follow-up period and to continue to complete the daily diary will be then included in the follow-up period (starting from visit V4) and will be randomly assigned to dispensing of product adequate for the next 12 weeks or to control group (i.e. no treatment). All patients included in the follow-up period received a dispensing of omeprazole adequate for the next 12 weeks, to be taken as rescue medication only if necessary and according to the Investigator's indications. The investigator explained to patients when and why omeprazole could be taken and that the intake and the reason will be to be reported in the daily diary. Then the investigator proceeded to:

- Patient's randomisation to Gerdoff® group or control group;
- Dispensing of the kit of Gerdoff® for the following 12 weeks of treatment to patients randomised in this group;
- Dispensing of the kit of omeprazole for the following 12 weeks of treatment to patients that continued in the follow-up period;
- Registration in the source document and in the eCRF of the number of product kit dispensed to responder patients in Group 1 that continued in the follow-up period;
- Registration in the source document and in the eCRF of the number of kit of omeprazole as rescue medication dispensed to all patients that continued in the follow-up period;
- Recommendation to take the first dose of investigational products in the morning of the day following Visit V4;
- Planning with the patient of the date for the following visit V5, which could be performed by phone. In this case, the Investigator dispensed to patients all required documents, i.e. the Likert scale, the RSI questionnaire and the diaries for visits V5 and V6, to be completed to perform visit V5 by phone;
- In case that visit V5 will be performed by phone, patients will be to be reminded that they had to return to the Investigator all documents received for the study.

Follow-up period

Visit 5 (T12 after 12 weeks \pm *3 days from the baseline visit): control visit*

Patients will be visited by a Gastroenterology specialist, who recorded all the following data collected during this visit (that could be performed by phone) in the source document and in the eCRF:

- Concomitant therapies, maintenance of the ongoing therapies, new therapies or changes in frequency or dosage of ongoing therapies, with particular attention to possible intake of nonpermitted medications;
- Assessment of upper symptoms associated with the diagnosis of GERD, by pointing into evidence possible changes from baseline and from end of study visit V4;
- RSI questionnaire, completed by patients during the visit. In case the visit will be conducted by phone, the patient will be reminded to return the diary to the investigational site in the following visit V6:
- Likert scale, completed by patients during the visit. In case the visit will be conducted by phone, the patient will be reminded to return the diary to the investigational site in the following visit V6;
- Compliance to treatment, based on verification of diaries. In case of necessity, the patient will be re-trained;
- Use of rescue medication: used products, frequency, dosage and reasons for intake;
- Possible incidents and/or adverse events: treatments/procedures taken to treat the event/incident, duration of the event/incident and correlation with the investigational product;
- Planning with the patient of the date for the following visit V6, and patient's remind to return all materials received for the study.

Visit 6 (T18 after 18 weeks \pm 3 days from the baseline visit): end of follow-up visit

Patients will be visited by a Gastroenterology specialist, who recorded all the following data collected during this visit in the source document and in the eCRF:

- Vital signs (systolic and diastolic blood pressure, heart rate, respiratory rate, weight and height with calculation of BMI);
- Concomitant therapies, maintenance of the ongoing therapies, new therapies or changes in frequency or dosage of ongoing therapies, with particular attention to possible intake of nonpermitted medications;
- Objective examination, by pointing into evidence possible changes from baseline;
- Assessment of upper symptoms associated with the diagnosis of GERD, by pointing into evidence possible changes from baseline and from visit V4;
- Haematology and blood chemistry: haemochrome, ESR, CRP, AST, ALT, alkaline phosphatase, gamma-GT, total and direct bilirubin, glycaemia, creatininemia, BUN, and changes from baseline;
- Evaluation of beta-hCG levels, only in women of childbearing potential;
- RSI questionnaire, completed by patients during the visit;
- Likert scale, completed by patients during the visit;
- Review of diaries and Investigator's assessment of diary entries;
- In case that visit V5 will be performed by phone, collection of the Likert scale, the RSI questionnaire and the diaries for visits V5;

- Compliance to treatment, collection of investigational products accountability of the product returned by patient during this visit;
- Use of rescue medication: used products, frequency, dosage and reasons for intake;
- Possible incidents and/or adverse events: treatments/procedures taken to treat the event/incident, duration of the event/incident and correlation with the investigational product;
- Assessment of maintenance of the effects based on data obtained from the RSI questionnaire and the Likert scale;
- End of follow-up assessments.

6.5.3 Study Endpoints

Primary performance variable

The primary performance variable of the study will be the change from baseline to visit V4 of the total score of RSI questionnaire, used to assess the effect of treatment on upper symptoms. The RSI questionnaire examines 9 items, to be scored from 0 to 5, with a higher score indication a higher severity of the symptom (range of total score: 0-45).

Secondary performance variables

The secondary performance variables of the study will be:

- Change of the total score of RSI questionnaire from baseline to the other time points;
- Change of the score of single items of the RSI questionnaire from baseline at any time point;
- Number and percentage of responder/non-responder patients at end of treatment (visit V4);
- Change from baseline to end of treatment (visit V4) and end of follow-up (visit V6) of upper symptoms, assessed using the Likert scale. The Likert scale scored symptoms from 0 to 4, with a higher score indication a higher frequency of the symptom;
- Presence of upper symptoms at baseline, end of treatment (visit V4) and end of follow-up (visit V6), assessed using the RSI questionnaire and the Likert scale:
- Use of rescue medication during the follow-up period: administered therapy, frequency of administration, timing of administration and administered dose;
- Patient's opinion of satisfaction with treatment, requested at intermediate Visits V2 and V3, and at the end of treatment visit V4, by means of a semiquantitative ordinal scale, where: 0 = low, 1 = discrete, 2 = good, 3 = excellent.

Safety variables

The safety variables of the study will be:

- Frequency of adverse events and incidents occurring at any time, during the study;
- Changes from baseline of haematology and blood chemistry parameters;
- Changes from baseline of vital signs (weight, BMI, blood pressure, heart rate and respiratory rate).

Incidents and adverse events

Incidents

According to MEDDEV 2.12.1, Rev. 8, a medical device incident is defined as 'any malfunction or deterioration in the characteristics and/or clinical performance of a device, as well as any inadequacy in the labelling or the instructions for use, which, directly or indirectly, might lead to or might have

led to the death of a patient, or a user or of other persons or to a serious deterioration in their state of health'.

A medical device incident that required reporting included:

- a) Serious public health threat: any event type which resulted in imminent risk of death, serious deterioration in state of health, or serious illness that required prompt remedial action (MEDDEV 2.12.1 rev.8).
- b) Death or unanticipated serious deterioration in state of health of a subject that resulted in:
 - 1) A life-threatening illness or injury, or
 - 2) A permanent impairment of a body structure or a body function, or
 - 3) In-patient or prolonged hospitalization, or
 - 4) Medical or surgical intervention to prevent life-threatening illness or injury or permanent impairment to a body structure or a body function
- c) Other events: events that had an established link between the device and the event.

Adverse events and serious adverse events

An Adverse Event (AE) will be defined as "any untoward medical occurrence in a patient or clinical trial subject administered a medicinal product and which will not necessarily have a causal relationship with this treatment".

An adverse event could therefore be any unfavourable and unintended sign (including laboratory abnormal finding), symptom, or disease temporally associated with the use of a medicinal product, whether or not considered as related to the investigational medicinal product.

A Serious Adverse Event (SAE)/Serious Adverse Drug Reaction will be defined as any untoward medical occurrence or effect that at any dose fell in one or more of the following categories:

- Resulted in death;
- Will be life-threatening;
- Required patient hospitalisation or prolongation of existing inpatients' hospitalisation;
- Resulted in persistent or significant disability or incapacity;
- Will be judged as clinically significant and/or as requiring a treatment and/or an intervention to prevent the above outcomes;
- Caused a congenital anomaly or birth defect;
- Caused the presumed transmission of an infective agent through the product.

Expectedness

An expected adverse event will be an adverse event, the nature or severity or consequence of which will be consistent with the applicable product reference safety information (Investigator's Brochure for an unapproved investigational product or Patient Information sheet for an authorised product). Expected adverse events that appears in a different mode of with a frequency higher than expected will be to be considered unexpected as well.

Intensity

Each adverse event will be rated on a 3-points scale of increasing intensity:

- Mild: the event presented with signs and symptoms that will be evident, but will be well tolerated;
- Moderate: the event caused discomforted that interfered with the usual activity of the patient;

- Severe: the event determined that the subject will be unable to work or to perform the usual daily activities.

Causality assessment

The relationship with the investigational product will be classified as follows:

- Related: following a careful evaluation, a certain relation with the use of the investigational product will be ascertained;
- Possibly related: following a careful evaluation, a possible relation with the use of the investigational product will be ascertained, but it will be not fully certain;
- Not related: the event will be not due to causes not related with the investigational product.

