1.3 Investigation Rationale

The aim of the present study will be to evaluate, in first diagnosed patients presenting with upper symptoms associated with GERD, the effect of a 6-week treatment with a combination based on CS, HA and aluminium hydroxide (Gerdoff®), co-administered with a treatment with PPIs, compared to treatment with PPIs as monotherapy, i.e. to verify, in patients treated with the combination of the two products, the reduction in symptoms frequency by means of a Likert questionnaire and the severity of upper symptoms by means of the Reflux Symptom Index (RSI) questionnaire (13), and to collect safety data. After 6 weeks of treatment, patients included in the two groups will be then classified as responders or non-responders. Responder patients will be defined as those patients that, at the 6th week of treatment, reached a RSI score decreased for at least 50% compared to baseline and an absolute value < 13.

Furthermore, the maintenance of the effect of treatment on the extra-oesophageal symptoms will be evaluated after a period of follow-up lasting 12 weeks, which could be entered only by responder patients randomised in the Gerdoff®-PPI arm. Patients included in the follow-up period will be randomised to receive Gerdoff® or no treatment (control group). Safety data will be also evaluated in the group of patients that continued in the follow-up period.

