2 STUDY OBJECTIVES

2.1 Primary Objective

The primary objective of this study will be to evaluate the efficacy of Gerdoff[®], a preparation based on CS, HA and aluminium hydroxide, in improving the upper symptoms in combination with a PPI (omeprazole) compared to treatment with PPI monotherapy (omeprazole), during 6 weeks of treatment and during the following 12-week maintenance follow-up period. The evaluation will be performed by means of the Reflux Symptom Index (RSI) questionnaire validated in Italian language.

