2.2 Secondary Objectives

The secondary objectives of the study will be to assess:

- The number and percentage of responders/non-responders at visit V4, after 6 weeks of treatment with Gerdoff®-PPI/PPI;
- The number and percentage of patients that maintained the effect of treatment at the follow-up visit V6, compared to the end of study visit V4, after 12 weeks of treatment with Gerdoff® or no treatment (control group);
- The percentage of reduction of symptoms' frequency in the two treatment groups, by means of a Likert questionnaire, at visit V4 after 6 weeks of treatment compared to baseline, and at visit V6 after 18 weeks of treatment compared to Visit V4;
- The overall patient's satisfaction of treatment, by means of a semiquantitative scale;
- The concomitant use of permitted and non-permitted rescue medications, during the first 6 weeks of treatment and the follow-up period;
- The safety of investigational products, evaluated by means of recording of changes in safety haematology and blood chemistry parameters and by collecting possible incidents/adverse events occurred during:
 - The first 6 weeks of treatment, for patients included in Group 2, PPI only, and for non-responder patients included in Group 1 (Gerdoff®-PPI);
 - During the overall 18-week study period for patients that continued with the follow-up period.

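### The follow-up objectives are set against V4, but the RSI and Likert change variables are measured from the pre-treatment baseline, so relapse within an arm can be tabulated as improvement

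*Combined protocol and SAP*

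**What the plan says.** **Objectives (section 2.2).** Two follow-up objectives use V4 as the reference. One is the number and percentage of "patients that maintained the effect of treatment at the follow-up visit V6, compared to the end of study visit V4". The other is the reduction in symptom frequency on the Likert questionnaire "at visit V6 after 18 weeks of treatment compared to Visit V4". Section 2.1 also extends the primary objective to the period "during 6 weeks of treatment and during the following 12-week maintenance follow-up period".

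**Variables (section 6.5.3).** The RSI total is listed as "Change of the total score of RSI questionnaire from baseline to the other time points", and the single RSI items are likewise taken from baseline. The Likert variable is "Change from baseline to end of treatment (visit V4) and end of follow-up (visit V6) of upper symptoms". Two further outcomes are not changes from baseline: the presence of upper symptoms at V1, V4 and V6, and "Use of rescue medication during the follow-up period".

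**Entry to follow-up (sections 1.3, 6.1 and 6.3.1).** Entry to the trial requires an RSI of at least 20. Only Group 1 patients classed as responders at V4 continue, meaning those who "reached a RSI score decreased for at least 50% compared to baseline and an absolute value < 13". They are then randomised 1:1, open-label, to Gerdoff or no treatment.

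**Procedures and analysis (sections 6.5.2 and 8.3.2).** At V5 and V6 the investigator notes symptom changes from baseline and from V4. At V6 the investigator also assesses maintenance from the RSI and Likert scores, but no criterion is given. Section 8.3.2 defines responders at V4 only, heads the Likert analysis as baseline to V4, and limits follow-up efficacy to descriptive statistics by group.

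**The concern.** The second randomisation can act only after V4, so for the follow-up question V4 is the starting point. Change from V1 adds together two things: the fall that qualified the patient for follow-up, and whatever happened afterwards. The first part is present in both arms by rule and is large.

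Because the follow-up is descriptive only, the within-arm tables are what a reader will use. As listed, they could show an untreated arm as improved although most of its effect has gone. The count of patients maintaining the effect, which is a stated objective, has no variable, criterion or planned summary behind it.

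**Working it through.** **The plan's own figure.** The only stated calculation is the sample size, which rests on the V4 comparison (delta 3.6, SD 5, 80% power, two-sided 5%). It reproduces: 2 × (1.960 + 0.842)² × 5² / 3.6² = 30.3, so 31 per arm and 62 in all; 62 / 0.8 = 77.5, so 78. Nothing below changes it.

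**Built-in fall.** Inputs: V1 at least 20 (section 6.3.1); V4 at most V1/2 and below 13 (section 1.3). The fall from V1 to V4 is at least V1/2, so at least 20/2 = 10 points for every patient in either follow-up arm.

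**What each reference shows.** Effect = V1 − V4; share lost = (V6 − V4) / (V1 − V4). The scores are illustrative and all satisfy the entry rules.

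| V1 | V4 | V6 | Share of effect lost | V6 − V1 | V6 − V4 | Responder rule met at V6 |
|---|---|---|---|---|---|---|
| 30 | 12 | 20 | 8/18 = 44% | -10 | +8 | no |
| 30 | 12 | 25.5 | 13.5/18 = 75% | -4.5 | +13.5 | no |
| 30 | 12 | 28 | 16/18 = 89% | -2 | +16 | no |
| 20 | 10 | 19 | 9/10 = 90% | -1 | +9 | no |
| 45 | 12 | 44 | 32/33 = 97% | -1 | +32 | no |

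The 25.5 is exactly 75% of the way back. With whole-number totals, 25 and 26 give 13/18 = 72% and 14/18 = 78% lost. In the last two rows the patient has only just qualified as a responder and can lose 90% to 97% of the effect while still showing a fall from V1.

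**Arm level, on assumed inputs.** The documents give no follow-up assumptions, so these are illustrative:

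- V1 about normal, mean 26, SD 5, kept within 20 to 45.
- V4 = 0.42 × V1 plus noise of SD 5, with the responder rule applied.
- 10 patients per follow-up arm.
- V6 = V4 + f × (V1 − V4) plus noise of SD 3, with f = 0.4 on Gerdoff and 0.8 on control.

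Means over 4,000 simulated trials:

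| | Gerdoff | Control | Difference |
|---|---|---|---|
| V6 − V1 | -11.1 | -3.7 | -7.4 |
| V6 − V4 | +7.4 | +14.8 | -7.3 |

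From V1 both arms look improved, and 88% of control patients score as improved. From V4 both arms have worsened. The between-arm difference is the same apart from simulation noise.

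**The case against.** **Not every V6 outcome uses V1.** Symptom presence at V6 and rescue use during follow-up are listed separately, and the visit procedures record changes from V4. This stands, and the point is limited to the RSI and Likert change variables. Neither separate outcome gives the Likert change from V4 or says what counts as maintained.

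**The data exist.** RSI and Likert are collected at V4 and V6, so the difference can be derived. This is true and makes the repair cheap. What is missing is a pre-specified variable and criterion.

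**A reader might infer that the treatment comparison is biased.** It is not. Patients are randomised at V4, so either reference estimates the same between-arm difference, and section 8.3.2 plans no follow-up test.

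**A reader might infer that the V4 reference is always more precise.** It is not. On assumed inputs (V1 about mean 26, SD 6, cut at 20; residual SD 4), worsening unrelated to the earlier gain gives an SD of 5.2 to 5.8 from V1 against 4.0 from V4. If patients return halfway to their own baseline, the SDs are equal at about 4.3 to 4.5. If 80% of the gain is lost, the order reverses: about 4.1 from V1 against 4.8 to 5.2 from V4.

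**Change from V1 is not false in itself.** In the first row of the patient table, 44% of the effect is lost and a real gain over V1 remains. It simply answers a different question from section 2.2.

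**Selection is on RSI, not Likert.** This stands. The guaranteed fall of at least 10 points applies to RSI only, since no Likert threshold governs entry. For Likert, what remains is the direct mismatch between sections 2.2 and 6.5.3.

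**Conclusion.** The point holds for the RSI and Likert change variables and for the missing maintenance count. Sections 2.2 and 6.5.3 use different reference visits, and section 8.3.2 does not reconcile them. A fall of at least 10 RSI points is built into both follow-up arms before the second randomisation, so within-arm change from V1 can show a loss of most of the effect as improvement.

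The 10-point floor and the patient table follow from the plan's own entry rules. The arm-level figures rest on assumed distributions and relapse rates and only illustrate the direction. The documents do not support a claim of bias between arms or of a general gain in precision.

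The point matters because stated secondary objectives would go unanswered, although the follow-up is descriptive and open-label. It does not touch the primary V4 comparison or the sample size. Section 8 cites a final SAP in Annex 10 whose separate text is not part of the material reviewed. If that text already defines these variables from V4, section 6.5.3 needs only to be aligned with it.

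**What to change.** **In section 6.5.3:**

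1. Define the V5 and V6 RSI change and the V6 Likert change for the follow-up as change from V4, in the patients re-randomised at V4 and by follow-up arm. Show each arm's V4 value beside it.
2. Keep change from V1 as a supplementary description.
3. Add the number and percentage maintaining the effect at V6 relative to V4, with all patients re-randomised at V4 as the denominator. One workable criterion is that the patient still meets the trial's own V4 responder rule on RSI at V6. Everyone meets it at V4, so the count reads directly as maintained or lost. Count early discontinuation as failure, as section 6.3.3 already states, and say how patients who used rescue medication are classified in this count.

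**In section 2.2:** the phrase "at visit V6 after 18 weeks of treatment compared to Visit V4" must be reconciled with section 6.4.2, where the control arm is untreated after V4.

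**Cost:** wording in two sections, a different reference column and one added row in the follow-up tables. No new visits, data or patients are needed. The follow-up figures will look less favourable than change from V1.
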